ACCORD	Academic and Clinical Central Office for Research & Development - Joint office for The University of Edinburgh and Lothian Health Board
CI	Chief Investigator
CRF	Case Report Form
GCP	Good Clinical Practice
ICH	International Conference on Harmonisation
PI	Principal Investigator
QA	Quality Assurance
REC	Research Ethics Committee
SOP	Standard Operating Procedure
ED	Emergency department
CBT	Cognitive Behavioural Therapy
EMERGE	Emergency Medicine Research Group Edinburgh
USA	United States of America
PHQ9	Patient Health Questionnaire 9
GOSE	Glasgow Outcome Scale Extended
EMA	Ecological Momentary Assessment

INTRODUCTION

1.1 BACKGROUND

Concussion is defined as a traumatically induced physiological disruption of brain function. This can occur in a wide range of circumstances from sports and military related injuries, assault, road-traffic accidents and falls. Reliable quantification of the public health burden of concussion is challenging because many patients do not present to healthcare services after sustaining one. However, it is clear that concussion and mild traumatic brain injury is the commonest reason for the under 65s to be admitted to hospital (Scottish Intercollegiate Guidelines Network, 2013). Estimates place the incidence at 300 people per 100 000 seeking medical attention however this varies internationally reflecting the availability of emergency medical services (Cassidy *et al.*, 2004). This incidence is believed to almost double when patients who do not seek medical attention are taken into account. Concussion does not cause the irreversible brain damage associated with more severe traumatic injuries but, there is growing evidence that patients may suffer from a constellation of physical, emotional and cognitive symptoms after a concussion. There is considerable controversy surrounding the natural history, mechanisms, causality and prognosis of post-concussion symptoms. A prospective cohort study of patients presenting to the emergency department after a concussion found that at 3 months 77% reported at least 1 post-concussion symptom (McMahon *et al.*, 2013). The impact of patients suffering from these symptoms on healthcare services is highlighted in a study by Hartvigsen and colleagues who found that over 90% of patients had sought care from at least one healthcare professional related to their symptoms at each of the 5 assessed time-points during the 1-year follow-up period (Hartvigsen *et al.*, 2014). Concussions also have been found to negatively impact on patients' quality of life and return to work (Emanuelson *et al.*, 2003; Graff *et al.*, 2019). In the NHS there is no coordinated clinical pathway for patients following a concussion.

Despite disagreement on the exact aetiology of post-concussion symptoms, there is a view that a complex interplay between biological, social and psychological factors drive the observed clinical phenotype. Therefore psychological interventions have been assessed to determine their value as therapies. Cognitive Behavioural Therapy (CBT) is a psychological intervention that uses personal coping strategies focusing on the interplay between behaviours, thoughts and feelings. There is a strong evidence base on the effectiveness of CBT in a range of mental health problems (Hofmann *et al.*, 2012). A systematic review found that CBT has been assessed in the context of concussion in 3 randomized controlled trials and concluded that it is likely to be effective in the treatment of post-concussion symptoms (Al Sayegh *et al.*, 2010). However, providing face-to-face therapy is highly labour intensive and there are considerable logistical and economic hurdles in delivering CBT for this patient cohort. Coupled to this, some patients do not wish to have face-to-face therapy sessions due to perceived stigma of talking therapies. Due to these difficulties, there have been efforts to use technology platforms as a means to overcome these barriers. One major success is the company Sleepio which has developed an automated CBT programme for patients with chronic insomnia. A clinical trial of Sleepio demonstrated that it improved sleep and daytime functioning (Espie *et al.*, 2012). Similarly, a systematic review of internet delivered CBT for anxiety and depression concluded that it was a promising alternative to face-to-face therapy (Ebert *et al.*, 2015). CBT therefore has the potential to be effectively delivered digitally and provide a scalable alternative to traditional CBT in the context of concussion.

1.2 RATIONALE FOR STUDY

Concussion is common and patients can go on to suffer with a constellation of symptoms which impacts their functional outcome and quality of life (McMahon *et al.*, 2013). Patient provision with information about their concussion and subsequent follow-up was highly variable in a prospective study in the USA (Seabury *et al.*, 2018). This is also the case with psychological therapies despite the fact there is evidence that CBT can help patients manage their symptoms after a concussion (Al Sayegh *et al.*, 2010).

We have developed HeadOn - a web application that delivers a CBT programme to patients following concussion. The application takes the patient through a 5-stage programme including: (i) understanding post-concussion symptoms; (ii) sleep after a concussion; (iii) lifestyle habits and exercise; (iv) managing negative thought patterns and (v) returning to baseline. The programme is delivered through a combination of weekly tasks (such as completing symptom diary, setting exercise goals and setting up a sleep time routine), audio/video media and reading material.

In this study, we would like to examine the feasibility of digitally delivering a course of CBT to patients following concussion. We hypothesise that patients will find it an acceptable and useful form of treatment. We plan on determining recruitment rates to guide future controlled trials.

2 STUDY OBJECTIVES

2.1 OBJECTIVES

2.1.1 Primary Objective

Our primary objective is to determine the following regarding the digital delivery of CBT to patients following concussion:

- Compliance of participants with a digital CBT program
- Usability of a digital CBT program as a form of therapy

2.1.2 Secondary Objectives

Our secondary objectives are:

- Determining functional outcome after the HeadOn program
- Determining the temporal profile of post-concussion symptoms, sleep disturbance and mood during the study period
- Identifying return to work rates
- Recruitment rates of patients presenting to a single emergency department

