3 STUDY DESIGN

The HeadOn feasibility study is a prospective feasibility study of patients presenting to the Edinburgh Royal Infirmary and St John's Hospital Emergency Departments (ED) (**Figure 1**). Patients will be identified from the ED. Potentially eligible patients will be contacted by a member of the Emergency Medicine Research Group Edinburgh (EMERGE) research team and their consent will be sought for participation. Those not recruited at presentation to the ED will be contacted by telephone, text or email within two weeks of their concussion date to seek their participation in the study, again by a member of the EMERGE research team. After consenting, the participant will be taken through the registration process for the HeadOn program. For patients who are contacted after discharge they will be taken through registration process over the telephone or if preferable will be able to return to the ED to go over the process.

At registration the participant will be invited to complete a series of patient reported measures including the Rivermead post-concussion questionnaire, Pittsburgh Sleep Quality Index, PHQ9 questionnaire and FAST alcohol questionnaire within the HeadOn program. Alongside this, a series of researcher-led anonymised data points will be collected in a separate specially designed database including demographics, date of concussion, neurological and imaging findings which will all be collected from the medical notes and imaging reports. The HeadOn program runs for five weeks following which the participant will be invited to complete the same set of outcome measures. Alongside this, all the participant will be contacted (via telephone, text or email) by a member of the research team at week 5 to complete a further five measurements: Glasgow Outcome Score Extended, mHealth App Usability questionnaire, time to return to work and a healthcare utility questionnaire. Interested participants will be invited back within two months of enrolling in the study for a more detailed qualitative interviews about HeadOn. The study will recruit for a period of 6-months or up to 100 participants.

[figure not shown]

Figure 1: Schematic of HeadOn study design

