6. DATA COLLECTION

Data will be collected at four points during the study period: at baseline, during the HeadOn program, at the final 5-week follow-up and during a voluntary qualitative interview. Two forms of data will be collected: patient-reported and researcher collected.

At baseline, participants will complete four patient questionnaires within the HeadOn program (Rivermead postconcussion, PHQ9, Pittsburgh Sleep Quality and the FAST alcohol screen). Researchers will also capture demographic, clinical and imaging findings data taken from participants notes and investigation finding reports. During the HeadOn program, participants will undergo a series of ecological momentary assessments (EMAs) aimed at capturing information about their symptoms, mood, thoughts about their concussion and behaviour (**Appendix**). This includes a symptom and mood diary which will be delivered daily. Alongside this, a series of other EMAs are delivered to the participant at different stages of the program (**Figure 2**): Stage 3 (Alcohol tracker), Stage 4 (Thought diary) and Stage 5 (Goal setting). HeadOn generates automated reminders (by email or notification) to help keep participants engaged. In the final 5-week follow-up of the study, both participant-reported and researcher collected outcome measures will be captured. Participants will complete the following questionnaires digitally through the HeadOn program: Rivermead postconcussion, PHQ9, Pittsburgh Sleep Quality and FAST alcohol screen. The participant will also be contacted by a trained member of the HeadOn research team to complete four questionnaires: the mHealth app usability questionnaire, healthcare utility, return to work questionnaire and the Glasgow Outcome Score Extended (GOSE). The participant will also be reminded to complete the week 5 patient-reported questionnaires if they had not already done so. If the participant has not completed these questionnaires by week 6, then they will be contacted again by a member of the research team to complete these questionnaires.

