8.2.4 Temporal change in secondary outcome measures

A number of secondary outcome measures are examined at both recruitment and at the 5-week follow-up (Rivermead post-concussion questionnaire, PHQ9 questionnaire, Pittsburgh Sleep Quality Index). We plan a descriptive analysis of the temporal changes in the aggregate scores of these measures.

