8.2.6 HeadOn symptom diary data

As part of our analysis, we aim to examine the association between data collected in the HeadOn symptom diary and functional outcome. Participants will be dichotomised based on their aggregate scores of the symptom diary. Logistic regression will then be used to examine its predictive relationship with GOSE outcome.

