Appendix VI: mHealth App Usability Questionnaire (Zhou et al., 2019)

The screenshot shows the HeadOn app interface. At the top, there is a navigation bar with icons for a menu, home, chart, and SOS. The main header says "Hello [name]". Below this, a large box displays "You are on Stage 5 (Day 125)" with a "Getting back to baseline" icon. It also shows a "Stage Introduction" video player with a progress bar at 0:00 / 2:22. To the right, there are sections for "Today's Reminders" (empty), "Today's Tasks" (with buttons for "Set your goal", "Complete Symptom Diary", and "View Course Progress"), and social sharing icons for Twitter and Email. At the bottom, there are links for "Terms & Conditions" and "Privacy Policy" and the "headon" logo.

Appendix VII: HeadOn homepage showing reminder/task sections alongside the weekly audio which introduces the stage.

How do you feel today?				
Headache?				
None				Severe
Dizziness				
None				Severe
Sleep Disturbance				
None				Severe
Fatigue				
None				Severe
Feeling irritable				
None				Severe
Low mood				
None				Severe
Poor memory				
None				Severe
Difficulty concentrating				
None				Severe

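### The objective asks for the course of symptoms, sleep and mood over the study, but section 8.2.4 gives only a two-point change and diary scores are not summarised over time

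*Combined protocol and SAP*

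**What the plan says.** - **Objective (2.1.2):** "Determining the temporal profile of post-concussion symptoms, sleep disturbance and mood during the study period".
- **Endpoints (2.2.2):** one questionnaire per domain, namely Rivermead for symptoms, PHQ9 for mood and the Pittsburgh Sleep Quality Index (PSQI) for sleep. The diary is not listed.
- **Analysis over time (8.2.4):** these "secondary outcome measures are examined at both recruitment and at the 5-week follow-up", and "We plan a descriptive analysis of the temporal changes in the aggregate scores of these measures".
- **Diary collection (section 6):** "This includes a symptom and mood diary which will be delivered daily". Section 1.2 instead gives the diary as an example of a weekly task. Section 3 sets the duration: "The HeadOn program runs for five weeks".
- **Diary content (Appendix VIII):** the form opens with "How do you feel today" and has eight items: headache, dizziness, sleep disturbance, fatigue, irritability, low mood, memory and concentration.
- **Analysis of diary scores (8.2.6):** "we aim to examine the association between data collected in the HeadOn symptom diary and functional outcome". The method is: "Participants will be dichotomised based on their aggregate scores of the symptom diary", followed by logistic regression on GOSE.
- **Other use of data entered in the app (2.2.1 and 8.2.3):** classification of compliance and a description of how participants interact with HeadOn.

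**The concern.** A profile during a period is a statement about shape: when scores fall, whether they level off, whether they rise again. Two measurements give one difference and no shape. The study collects repeated same-day ratings that could show the shape, but the one analysis of those ratings collapses them over time before use. Followed as written, the plan would report how far participants had moved by week 5 and nothing about how they got there. The data that could fill the gap would already have been collected.

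**Working it through.** The plan states no figure to reproduce. The check sets the objective against each analysis in 8.2 and counts occasions.

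**1. Which analyses describe symptoms, sleep or mood over time?**

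| Section | Content | Time dimension for these domains |
|---|---|---|
| 8.2.1 | Demographics, clinical and imaging findings | None |
| 8.2.2 | Recruitment rate | None |
| 8.2.3 | Compliance groups and interaction with the app | Engagement only |
| 8.2.4 | Rivermead, PHQ9, PSQI | 2 occasions |
| 8.2.5 | GOSE, with admission predictors | None |
| 8.2.6 | Dichotomised diary aggregate against GOSE | Collapsed to 1 binary value per participant |

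No section plans a summary of diary scores by day, week or stage.

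**2. Occasions available.**
- Questionnaires: 2 per participant, giving 2 − 1 = 1 change score.
- Diary, if daily: at most 5 weeks × 7 days = 35 entries.
- Diary, if weekly: about 5 entries.

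The daily figure is a ceiling, because actual entries depend on engagement, which is itself a primary endpoint. Either frequency exceeds two.

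**3. What two occasions cannot distinguish.** Let a participant start at score S. Participant A falls to S/2 by day 7 and stays there. Participant B stays at S until week 4 and then falls to S/2. Both show a change of S/2 − S = −S/2 under 8.2.4, although their courses differ.

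**4. Does the diary cover the three domains?** Yes. It has one item on sleep disturbance, one on low mood, and six on other symptoms (1 + 1 + 6 = 8). It is narrower than the questionnaires: the Rivermead has 16 items, and a single item does not stand in for the PSQI or PHQ9.

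**5. Recall windows at recruitment (supporting check).** The PSQI asks about the past month, and HeadOn starts 0 to 14 days after injury (4.2). Taking a month as 30 days, which is an assumption, the share of the baseline window before injury is (30 − d)/30 for a start on day d:
- d = 0: 30/30 = 100%
- d = 14: 16/30 = 53%

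The PHQ9 asks about the last 2 weeks, so its share is (14 − d)/14, from 100% at d = 0 to 0% at d = 14. The first sleep point therefore describes mostly time before the injury. The diary's same-day question does not have this feature.

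**6. Which time axis?** With 35 days of programme, a participant starting on day 0 covers weeks 1 to 5 after injury. One starting on day 14 covers days 15 to 49 (14 + 35 = 49), which is weeks 3 to 7. Both can contribute only in weeks 3 to 5. A display by week since injury alone would mix a change in who contributes with a change in symptoms. Programme week avoids that, but puts participants up to 14 days apart in recovery at the same point. Showing early and late starters separately deals with this.

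**The case against.** The strongest defence is that objective, endpoints and analysis form a consistent chain: 2.2.2 names one instrument per domain and 8.2.4 analyses exactly those three. On this view the only dispute is whether a profile needs more than a before-and-after comparison. Much of this stands. A reader might infer that the objective goes unanalysed or cannot be met at all. The documents do not support that, because 8.2.4 serves it in part. What remains is the gap between a profile during the study period and a net change.

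A reader might also infer that the diary is unused. That is not so. Its scores enter 8.2.6, and as a programme task its entries count towards compliance in 2.2.1 and 8.2.3. The accurate statement is that its scores are never described over time.

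Two further limits are fair. The diary is a component of the intervention and not a listed endpoint, so it can only supplement the questionnaires. And the future-trial purpose stated in 1.2 concerns recruitment rates, so the point should not be rested on a claim that this study is meant to set the timing of a later trial's outcome assessment. Neither limit removes the mismatch with 2.1.2.

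**Conclusion.** The point holds as a mismatch between one secondary objective and its analysis. The plan delivers a two-point change in three questionnaires and says nothing about the course between recruitment and week 5. The diary could supply about 5 to at most 35 further occasions per participant in all three domains, and no section of 8.2 summarises it over time.

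The consequence is moderate. This is a descriptive secondary objective in a feasibility study, and the primary endpoints and recruitment target are untouched. The change is still worth making, because it would let the study answer its own objective from data it already collects.

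The conclusion assumes that profile means more than a net change. It does not depend on whether the diary is daily or weekly, nor on the recall-window check, which only strengthens the case for sleep.

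**What to change.** Add to 8.2.4 a descriptive summary of diary scores by programme week that:
- shows sleep disturbance and low mood separately from the other symptoms;
- gives the number of participants contributing in each week;
- splits the curves by how long participants kept the diary, so that dropout is not read as recovery;
- takes account of time from injury to start, for example by showing early and late starters separately, so that staggered entry is not read as recovery. The date of concussion is already collected (section 3).

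Keep the Rivermead, PHQ9 and PSQI comparison as the net-change summary. Reconcile 1.2 and section 6 on whether the diary is weekly or daily.

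The cost is one descriptive analysis of data already collected. The small downside is that entries come mainly from engaged participants, so the profile describes diary users and should be labelled that way. The counts and the split by diary length make this selection visible but do not remove it.

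If the summary is not added, narrow the objective in 2.1.2 to change from recruitment to week 5, so that it matches the analysis.

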2.2 ENDPOINTS

2.2.1 Primary Endpoint

1) Participant compliance with CBT program

Data inputted into the digital CBT program will be used as surrogate marker of participant compliance. During each stage of the program participants are required to input data as part of the CBT tasks. Participants will be divided into the following three groups: *Fully compliant*: participants who input data into the program during all five stages; *Partially compliant*: participants who input data but not during all five stages; *Non-compliant*: participants who do not enter any data into the program

2) mHealth App Usability Questionnaire

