8.2.3 Patient compliance

During each stage of the program participants are required to input data as part of the CBT tasks. Participants will be divided into the following three groups:

- a) *Fully compliant*: participants who input data into the program during all five stages
- b) *Partially compliant*: participants who input data but not during all five stages
- c) *Non-compliant*: participants who do not enter any data into the program

We plan to conduct simple descriptive analysis to better understand trends in patient interaction with HeadOn.

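### As worded, the primary compliance rule counts any data entered into HeadOn, so a participant who completes only the baseline questionnaires is partially compliant rather than non-compliant

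*Combined protocol and SAP*

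**What the plan says.** Section 2.2.1 makes data entered into the digital program the surrogate for compliance. It explains that "During each stage of the program participants are required to input data as part of the CBT tasks" and then defines three groups. Fully compliant means "participants who input data into the program during all five stages" (the wording is the same in 8.2.3). Partially compliant means some data, but not in all five stages. Non-compliant means "participants who do not enter any data into the program". Section 8.2.3 repeats the groups for the analysis and adds no restriction on the type of entry.

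Other sections put questionnaire data in the same program. Section 3 has participants complete the Rivermead, the Pittsburgh index, the "PHQ9 questionnaire and FAST alcohol questionnaire within the HeadOn program" at registration. Section 6 confirms this: "At baseline, participants will complete four patient questionnaires within the HeadOn program". For follow-up, Section 3 says "The HeadOn program runs for five weeks following which the participant will be invited to complete the same set of outcome measures", and Section 6 says "Participants will complete the following questionnaires digitally through the HeadOn program". Staff prompt the follow-up forms: "The participant will also be reminded to complete the week 5 patient-reported questionnaires if they had not already done so", with a further contact if they are still missing at week 6.

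**The concern.** The endpoint is meant to show whether patients engage with a CBT program. Baseline questionnaires are outcome measurement, not therapy, and Section 3 has them offered at registration, a process that staff take the participant through. If they count as data in the program, the group that should show failure to engage excludes exactly the people who enrolled, filled in the forms and did nothing more. Compliance is one of the two parts of the primary objective (2.1.1), so this affects a headline result. Two competent analysts could also report different proportions from the same export, one counting every entry and the other only task entries. The plan does not settle who will make that choice: 7.2 gives the analysis to the study statistician and 8.2 to the study PI.

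**Working it through.** The plan states no expected or target compliance rate, so there is no figure of its own to reproduce. The check is a classification, followed by simple arithmetic on assumed counts.

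**Step 1: what the definitions require.** Non-compliant needs zero entries of any kind in the program. Partially compliant needs at least one entry and fewer than five stages covered, and fewer than five includes none.

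**Step 2: what is entered in the program.** Under Sections 3 and 6: the four baseline questionnaires, the daily symptom and mood diary, the stage tasks (alcohol tracker, thought diary and goal setting in stages 3, 4 and 5), and the four week-5 questionnaires.

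**Step 3: classify typical participants.**

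| Entries made | Literal wording | CBT-task entries only |
|---|---|---|
| None | Non-compliant | Non-compliant |
| Baseline questionnaires only | Partially compliant | Non-compliant |
| Baseline and week-5/6 questionnaires, no task | Partially compliant | Non-compliant |
| Tasks in all five stages | Fully compliant | Fully compliant |

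The second and third rows move. Both follow from the baseline forms alone, so neither depends on how the week-5 forms are treated.

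**Step 4: size.** Let T be the number who do no CBT task, and b the number of those who complete the baseline questionnaires and so leave the non-compliant group. Then

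literal non-compliant = T − b.

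The denominator is the recruitment target of 100 (4.1, 8.1). T and b are assumptions, because the documents give neither. With T = 20:

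- b = 5: 20 − 5 = 15, reported as 15%
- b = 10: 20 − 10 = 10, reported as 10%
- b = 20: 20 − 20 = 0, reported as 0%

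If every participant completes baseline, then b = T and the literal rate is 0% whether T is 10, 20, 30 or 40. This shift comes from the definition and does not shrink with a larger sample.

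**The case against.** The strongest reply is context. The sentence on CBT tasks comes directly before the three groups in both sections, and the endpoint is titled as compliance with the CBT program. Section 6 also lists baseline, in-program data, 5-week follow-up and interview as four separate collection points, and Table 1 gives time 0 and close-out their own columns. A sensible analyst would probably count task entries only. As evidence of intent, this stands. It does not limit the rule: the sentence says what participants must do, not which entries count, and the non-compliant definition turns on the absence of any data. Figure 2 is not shown in the text available for this review and may make the split clearer.

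A reader might go further and infer that prompted week-5/6 questionnaires will be credited as stage 5 input and inflate full compliance. The documents do not support that. Section 3 places those forms after the five-week program, and Section 6 and Table 1 separate them from it. What remains is loose wording: they are entered through the program and no sentence excludes them.

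A reader might also infer that stage 5 stays open for months, and longer for early recruits, because the Appendix VII homepage shows Stage 5 at day 125 and 12.6 restricts access only once the study is completed. The screenshot may be a demonstration account, and 12.6 sets no counting rule. All that can be said is that no cut-off for late stage entries is stated. Counting registration fields as program data is not needed for the point either, since Section 6 describes them as going into the system.

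Finally, the counts in the working are assumed. They show the direction of the error and how it would scale, not its likely size.

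**Conclusion.** The point holds for the baseline questionnaires. Under the wording of 2.2.1 and 8.2.3, a participant who completes only those forms is partially compliant, so non-compliance with the CBT program is understated by the number of such people. The group could be nearly empty if most participants complete baseline. This rests on the literal wording; the likely intent is narrower, and the text does not show that the team will count questionnaires.

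The lesser point is that the status of the week-5/6 questionnaires and of late stage entries should be stated. The documents do not establish that either will inflate the fully compliant group.

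The size is unknown because no compliance rates are given. No compliance target exists, so no stated decision changes. The effect is on a reported primary result, which makes the definition worth correcting before the data are analysed.

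**What to change.** In 2.2.1 and 8.2.3, keep the three groups and add a rule on qualifying entries:

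- Classify participants only on CBT-task entries, including the symptom diary, made during the program stages.
- State that registration fields, the baseline questionnaires and the week-5/6 questionnaires do not count.
- Report entries made after the five-week program separately. Someone who finishes stage 5 late is then still visible without altering the main classification.

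The cost is a wording change in two sections and a filter on the HeadOn export by entry type and date. The five-stage rule already needs the stage or date of each entry. The documents do not describe the export's fields, so availability of entry type and date should be confirmed. No extra data collection is expected. The downside is that reported compliance may be less favourable.
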